2 INTRODUCTION: BACKGROUND INFORMATION AND SCIENTIFIC RATIONALE

2.1 Background Information

Periodontitis is among the most prevalent causes of years lived with disability among adults worldwide (GDB Collaborators 2020). Periodontitis is a bacterial inflammatory disease that has been reported to affect nearly 40% of Americans aged 30 years or older (GDB Collaborators 2020). If left untreated, periodontitis can lead to tooth loss and patient-perceived morbidity (Eke et al. 2018). Historically, antibiotic use has been an integral part of periodontal disease treatment. However, antibiotic stewardship calls for optimizing antibiotic prescribing to effectively treat infections, reduce antibiotic misuse, and prevent the development of antibiotic-resistant microbial strains (Dinsbach 2012, Doron & Davidson 2011, Sabtu et al. 2015). Since 2015, the American Dental Association (ADA) developed evidence-based guidelines limiting circumstances for prophylactic antibiotic use in dental practice (Sollecito et al. 2015, Lockhart et al. 2019); however, evidence regarding antibiotic use in the treatment of periodontal infections is considered weak because of substantial inconsistencies across small scale trials (Smiley et al. 2015). Further, existing trials are underpowered to assess the effects of disease- and patient-related factors to adjunctive antibiotic benefit, therefore, dentists are left to decide when adjunctive antibiotics are indicated, and which dental patients need them to achieve periodontal health (Smiley et al. 2015). In the context of periodontitis treatment, a biological rationale exists to support adjunctive antibiotic use to reduce periodontal pathogenic bacteria, but clinical trials assessing adjunctive antibiotic effectiveness have presented varying results depending on the study, sample population and disease characteristics (Hafajee et al. 2003, Hafajee et al. 2007, Teughels et al. 2020). Nonetheless, data from academic studies suggest that adjunctive systemic antibiotics may be beneficial for certain populations only, as the biological response to treatment is highly variable across individuals (Smiley et al. 2015). This marked variability warrants the identification of person and/or diseaserelated characteristics that are linked to maximum benefit from adjunctive antibiotic treatment. Consequently, guidelines may be established with tailored indications for their use with the goal of minimizing antibiotic misuse in periodontal treatment to avoid development of antibiotic resistance while optimizing outcomes (Garcia et al. 2013).

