Step 1: Identify periodontal patients who need to receive a minimum of two quadrants of SRP for periodontal treatment.

Step 2: Evaluate medical history (ASA status) and age inclusion requirements.

Step 3: Confirm that the rest of the eligibility criteria are met, via an electronic screening questionnaire, and as per the screening table below.

Patient participant eligibility Criteria

- At least 40 years of age
- ASA Class I or II
- ≥ 20 teeth, excluding third molars
- Needs periodontal care for Generalized stage II-III, Grade A-C periodontitis
- Indicated to receive SRP in a minimum of 2 quadrants with CDT code 4341
- If diabetic, HbA1c is ≤ 10%
- Willing and able to provide informed consent

- Is NOT currently pregnant or breastfeeding
- Does NOT have a known drug allergy to antibiotic or anesthetics
- No systemic antibiotics within the last 3 months
- No medical condition that requires antibiotic prophylaxis prior to receiving dental treatment

Patient participant Retention: We have estimated for 20% attrition at 12 months. Because the primary endpoint occurs 12 months following treatment and because periodontal patients are usually lifetime patients where maintenance visits are an integral part of periodontitis management, we believe the attrition rate is reasonable. To minimize loss to follow-up, we will work with the study management team at the NCC and regional Node staff to increase retention including study visit reminders to practitioners and patient participants.

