Given the complexity of the correlation structure present in periodontal PD data, the variability in the number of probing sites a given patient participant presents with, and the variability of the correlation in sites depending on which teeth are present, a custom simulation was conducted to further explore the power of this design. In the simulation, patient participants are added to the study with a random number of existing teeth ranging from twenty to twenty-eight, with anterior teeth being added with greater probability than posterior teeth. In order to assign baseline PDs, a correlation structure was constructed in which sites on the same teeth are more highly correlated with each other and sites on different teeth are assigned a correlation based on the distance between them. Simulated baseline PDs are then added with an average depth of 4.5 mm. Similarly changes from baseline were simulated using a similar correlation structure with an average change of 0.3 mm being assumed for the placebo group, a 0.5mm in the AMXM group), and a standard deviation of 1 mm for both groups. This difference of 0.2 mm was chosen as it was determined to be a small but clinically meaningful difference. This synthetic data was then analyzed using the hierarchical model described in section 12.4. The simulation suggested that a sample size of N=220 per arm would be sufficient to achieve 90% power for detecting an average reduction of PD=0.2 mm. Sensitivity analyses were conducted which suggested that by choosing to design the study to a relatively high power of 90%, the design is likely to have adequate power of >80% even if the observed correlation in the study, observed average number of teeth remaining, or the positioning of remaining teeth deviate from that which was included in our initial simulation by a moderate amount. After accounting for a potential dropout rate of 20% and to distribute an even number of patient participants across thirty-four practitioners, the final total sample size would be N=544 or 272 per arm.

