Sensitivity of the analysis to model misspecification and potential site (provider) effects will be investigated by assessing the cluster-bootstrap stability of the analysis. Any deviations impacting performance will be mitigated by modification of the primary analysis potentially to an approach utilizing the Huber-White sandwich estimator for the variance.

Missing data

For all patient participants, we will attempt to gather follow-up information and reasons for dropout regardless of protocol completion and censor at the point of drop out. PBRN studies routinely attempt to collect reasons for dropout. We will compare baseline data between those with and without missing data and examine whether there are variables that are related to missingness. For each independent variable in the data set, the degree of missingness will be assessed. For key independent variables (demographics, and variables directly relevant to the analyses outlined above), variables with missingness will be dealt with using multiple (greater than or equal to 10) imputation by

chained equations and an appropriate variance will be derived using Rubin's rules (Azur et al. 2011).

Missing outcome variables will not be imputed for analysis. If for a given outcome variable less than 5% of the observations are missing, the missing observations will be dropped. If more than 5% of the outcome variables are missing and the study is positive (demonstrates a benefit for the treatment group over the control), subsequent tipping point analyses will be conducted to determine the potential influence of the missingness on the analysis. Tipping point analyses are used to determine how contrary to the observed data the missing data would need to be in order to reverse the findings of the study. This analysis will be conducted by fitting a predictive model to the observed study data and then using a modified version of that model to impute missing outcomes under progressively increased pessimism until the positive effect observed in the study is countered. This gives the reader an idea of how extremely contrary the missing outcomes would need to be in order to have been influential.

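### The stated sensitivity analysis for missing outcomes runs only after a positive result and only in the pessimistic direction, so a null 12-month result has no planned re-estimation under non-random dropout

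*Protocol*

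**What the plan says.** The rule is in the missing-data part of protocol section 12.4.

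- On the main analysis: "Missing outcome variables will not be imputed for analysis". Below 5% missing, the missing observations are dropped.
- Above 5%, a tipping-point analysis follows under a double condition: more than 5% of the "outcome variables are missing and the study is positive (demonstrates a benefit for the treatment group over the control".
- It runs one way. A model fitted to the observed data is modified to "impute missing outcomes under progressively increased pessimism until the positive effect observed in the study is countered".
- Whatever the result, reasons for dropout are sought, and "We will compare baseline data between those with and without missing data and examine whether there are variables that are related to missingness".
- Multiple imputation is reserved for independent variables.
- The other sensitivity work has a different target: "Sensitivity of the analysis to model misspecification and potential site (provider) effects will be investigated by assessing the cluster-bootstrap stability of the analysis".

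On expected missingness, section 5.3 says "We have estimated for 20% attrition at 12 months", and section 12.2 sizes the trial "After accounting for a potential dropout rate of 20% and to distribute an even number of patient participants across thirty-four practitioners".

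On purpose, section 2.1 hopes that "guidelines may be established with tailored indications for their use with the goal of minimizing antibiotic misuse", and section 2.2 presents confining antibiotics to uses where evidence supports them as a priority.

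**The concern.** The case of more than 5% missing with a result that is not positive gets no sensitivity analysis in the protocol. It is a likely case, because planned attrition is four times the threshold. A check on an untestable assumption should not depend on how the test came out.

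Non-random dropout can mask a benefit as well as create one. Suppose placebo participants whose pockets deepen after the 6-week visit are the ones who leave. The remaining placebo group then looks better than it should, and the observed difference shrinks. Making the imputed values more pessimistic for the antibiotic arm cannot reveal this, since it only moves a null result further towards null.

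At stake is how firmly a null result can be read. In a trial motivated by antibiotic stewardship, readers will want to know whether a finding of no detectable benefit could reflect who was lost to follow-up.

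**Working it through.** **1. The plan's own figures.** Section 12.2 gives 220 per arm for 90% power at 0.2 mm, then 20% dropout.

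- 220 / 0.8 = 275 per arm, 550 in total. The stated 272 per arm and 544 in total (34 × 16) are 1.1% lower, which the even split across practitioners explains.
- Expected completers: 272 × 0.8 = 217.6 per arm.
- Expected missing at 12 months: 0.20 × 544 = 108.8, about 109 participants, against a trigger of 0.05 × 544 = 27.2.

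The sample size is not in dispute.

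**2. Standard error (assumption).** The 220 comes from a site-level simulation whose correlations are not given, so the SE must be back-solved. With two-sided alpha 0.05 and 90% power:

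SE = 0.2 / (1.960 + 1.282) = 0.0617 mm, or 0.062 rounded.

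This corresponds to a patient-level SD of 0.647 mm with 220 per arm. With 217.6 completers, SE = 0.647 × √(2/217.6) = 0.0620 mm and power is 89.7%.

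**3. How dropout can produce a null.** Let c be the between-arm difference in completers and c + d that in dropouts. With 20% missing and a true overall effect of 0.2 mm:

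0.8c + 0.2(c + d) = 0.2, so c = 0.2 − 0.2d.

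Chance of significance = Φ(c / 0.0617 − 1.96).

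| Excess d (mm) | Completers c (mm) | Dropouts c + d (mm) | Chance of significance |
|---|---|---|---|
| 0 | 0.20 | 0.20 | 90% |
| 0.1 | 0.18 | 0.28 | 83% |
| 0.2 | 0.16 | 0.36 | 74% |
| 0.3 | 0.14 | 0.44 | 62% |
| 0.4 | 0.12 | 0.52 | 49% |

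Using 0.0620 instead changes these by at most one percentage point. The values of d are assumptions; the protocol gives none. The table also assumes that the dropouts' 6-week data carry no information about their 12-month values.

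**4. Tipping points on each side of significance.** With SE 0.0620, held fixed for simplicity, the smallest significant difference is 1.96 × 0.0620 = 0.122 mm (0.1216 unrounded). The difference in dropouts that brings the whole-sample estimate to that boundary is (0.1216 − 0.8 × observed) / 0.2.

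| Observed in completers (mm) | Needed in dropouts (mm) | Departure from completers (mm) |
|---|---|---|
| 0.05 (null) | 0.408 | +0.358 |
| 0.08 (null) | 0.288 | +0.208 |
| 0.10 (null, p = 0.107) | 0.208 | +0.108 |
| 0.15 (positive) | 0.008 | −0.142 |
| 0.20 (positive) | −0.192 | −0.392 |

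On these assumptions, a near-miss null of 0.10 mm is more easily overturned than a positive result of 0.15 or 0.20 mm. Only the positive results would be examined under the plan.

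**The case against.** The other side has several good points.

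- **Dropout is not ignored after a null.** Reasons for leaving and predictors of missingness are examined whatever the result. A reader might infer that a null goes wholly unchecked, and the text does not support that. What stands is that these steps are descriptive and never re-estimate the treatment effect.
- **The primary model uses partial data.** A participant lost after 6 weeks still contributes baseline and 6-week depths. Poor response already recorded at 6 weeks is handled under missing at random. Only unrecorded later deterioration remains, so the table in step 3 is an unfavourable case. Masking (section 5.4.2), and follow-up continuing after the study drug is stopped (sections 5.5.2 and 6.3), also make differential dropout less likely. None of this tests the assumption.
- **The departures are hypothetical.** At d = 0.3 mm the dropouts would show a 0.44 mm difference, above the 0.4 mm meta-analytic effect that section 12.2 calls relatively large. It would be wrong to pick out 62% as an expected loss. Nor would a sensitivity analysis restore power; the table measures possible bias, not the cost of the rule.
- **Custom and hypothesis.** Tipping-point analysis is usually aimed at positive claims, section 12.1 states a superiority hypothesis, and a null would be reported with a 95% confidence interval. That interval shows sampling error but not the effect of non-random dropout.
- **The SAP is not shown.** It may add analyses, so one cannot say that no other sensitivity analysis exists. The conditional rule is nevertheless fixed in the protocol.

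**Conclusion.** The point holds as a gap in robustness. As written, the protocol's stated sensitivity analysis for missing outcomes depends on a positive result and runs in one direction. At the planned 20% attrition, a null 12-month result would have no planned re-estimation under non-random dropout.

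The possible size, for departures of 0.1 to 0.4 mm, is a fall in the chance of a significant 12-month result from 90% to between 83% and 49%. This rests on the back-solved SE, a true overall effect of 0.2 mm and uninformative 6-week data. It applies to 12 months only, since no attrition rate is given for 6 weeks.

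A reader might go further and infer that a null would steer antibiotic use just as strongly as a positive result, or that the trial is biased towards a null. The first is a judgement: the stewardship rationale makes a null relevant, but the protocol does not say how it would be acted on. Nothing in the protocol shows the second. This is a cheap improvement, not an error in the sample size, alpha or primary estimate.

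**What to change.** In section 12.4, remove the requirement that the study be positive. Whenever more than 5% of the primary outcome is missing, run the delta-adjusted analysis whatever the result, over a prespecified grid of shifts in both directions for each arm, and report where the conclusion changes. Removing the condition alone would not be enough, because a pessimistic-only search cannot challenge a null.

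The change should be made before unblinding; added after a null, it would look driven by the result.

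The cost is additional imputation runs, since a grid by arm is two-dimensional, and a table or two. Confining it to the primary outcome keeps this small. The sample size, alpha and primary estimate stay as they are.

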13 SOURCE DOCUMENTS AND ACCESS TO SOURCE DATA/DOCUMENTS

NCC Study staff, dental practices and the PI's local study team will maintain appropriate medical/dental and research records for this study, in compliance with ICH E6, Section 4.9 and regulatory and institutional requirements for the protection of confidentiality of patient participants. NCC Study staff, dental practices and the PI will permit authorized representatives of NIDCR and regulatory agencies to examine (and when required by applicable law, to copy) research records for the purposes of quality assurance reviews, audits, and evaluation of the study safety, progress, and data validity.

Data will generally be collected on eCRFs entered directly into the electronic data capture system, and consequently the eCRF will serve as the source document.

A summary of Source Data/Documents includes:

- Plaque biospecimen data will be entered into a registry maintained by the PI including the participant ID, collection timepoint and when available bacterial DNA extraction information. This registry will serve as the source document for the biospecimen data
- Consent forms via EDC
- Registration / Contact forms via EDC
- Medical/Dental History
- Study case report forms via EDC
- Periodontal measurements extracted from uploaded periodontal charts and entered into the EDC.
- Protocol deviation logs
- Safety event forms via EDC
- Participant withdrawal form via EDC

14 QUALITY CONTROL AND QUALITY ASSURANCE

Quality Management (QM) is the overall process of establishing and ensuring the quality of processes, data, and documentation associated with clinical research activities. It encompasses both quality control (QC), and quality assurance (QA) activities. Quality management processes involve review of consent procedures and CRFs for completeness, timeliness, and accuracy; if irregular trends or other ongoing issues are identified, virtual or in-person monitoring visits may be conducted. The NCC, with input from the study team and ARC, has developed a study-specific Data Quality Management Plan (DQMP) that sets up a continuous quality control process with the goal of reducing the turnaround time between error detection and correction. Refer to the DQMP for further details on the quality management plan.

The NCC will develop a data management system for study data collection and safety event reporting. Study progress and safety will be reviewed monthly by the PI utilizing reports provided by the NCC. The PI will maintain primary responsibility for reporting of safety events to ensure patient participant safety and reviewing protocol deviations and considering study modifications if needed to ensure data integrity.

Study data will be entered directly onto eCRFs by the practitioner/designated office staff or patient participant via the NCC-managed study-specific electronic data system. The EDC provides: 1) an intuitive interface for validated data entry; 2) audit trails for tracking data manipulation; 3) access to study datasets that can be imported into common statistical packages; and 4) procedures for importing data from external sources.

15 ETHICS/PROTECTION OF HUMAN SUBJECTS

15.1 Ethical Standard

The PI, study team, and ARC and NCC personnel will ensure that this study is conducted in full conformity with the principles set forth in The Belmont Report: Ethical Principles and Guidelines for the Protection of Human Subjects of Research, as drafted by the US National Commission for the Protection of Human Subjects of Biomedical and Behavioral Research (April 18, 1979) and codified in 45 CFR Part 46 and/or the ICH E6.

15.2 Institutional Review Board

The protocol, informed consent form(s), recruitment materials, and all participant materials will be submitted to the National Dental PBRN central IRB for review and approval. Approval of both the protocol and the consent form(s) must be obtained before any participant is enrolled. Any amendment to the protocol will require review and approval by the central IRB before the changes are implemented in the study.

15.3 Informed Consent Process

Informed consent is a process that is initiated prior to the individual agreeing to participate in the study and continues throughout study participation. Extensive discussion of risks and possible benefits of study participation will be provided to patient participants and their families, if applicable. A consent form describing in detail the study procedures and risks will be given to the patient participant. Consent forms will be IRBapproved, and each patient participant is required to read and review the document or have the document read to him or her. The practitioner or designee will explain the research study to the patient participant and answer any questions that may arise. The patient participant will sign the informed consent document prior to any study-related assessments or procedures. Patient participants will be given the opportunity to discuss the study with their surrogates or think about it prior to agreeing to participate. They may withdraw at any time throughout the course of the study. A copy of the signed informed consent document will be given to patient participants for their records. The rights and welfare of the patient participants will be protected by emphasizing to them that the quality of their clinical care will not be adversely affected if they decline to participate in this study. No further data collection will occur for research purposes; any data collected prior to withdrawal will be used for missing data imputation.

The consent process will be documented in the clinical or research record.

15.4 Exclusion of Women, Minorities, and Children (Special Populations)

Any sex, gender, or racial/ethnic group of practitioners and patient participants (proportional to the composition of the participating dentist's patient population) may participate in this study. However, as per the exclusion criteria, women who are currently pregnant or lactating may not be considered for this study. Children are excluded from this study, as it is atypical for this age group to exhibit stage II-III

periodontitis. Young adults <40 years will be excluded to eliminate rare cases of substantial periodontitis, which may be associated/ related to systemic diseases.

15.5 Subject Confidentiality

Subject confidentiality is strictly held in trust by the investigators, study staff, and the study sponsor(s) and their agents. This confidentiality is extended to cover testing of biological samples and genetic tests in addition to any study information relating to patient participants.

The study protocol, documentation, data, and all other information generated will be held in strict confidence. No information concerning the study, or the data will be released to any unauthorized third party without prior written approval of the study sponsor.

The study monitors or other authorized representatives of NIDCR may inspect all study documents and records required to be maintained by the PI, including but not limited to, medical records (office, clinic, or hospital) for the study patient participants. The clinical study site will permit access to such records.

Certificate of Confidentiality

To further protect the privacy of study patient participants, the Secretary, Health and Human Services (HHS), has issued a Certificate of Confidentiality (CoC) to all researchers engaged in biomedical, behavioral, clinical, or other human subjects research funded wholly or in part by the federal government. Recipients of NIH funding for human subjects research are required to protect identifiable research information from forced disclosure per the terms of the NIH Policy (https://humansubjects.nih.gov/coc/index). As set forth in 45 CFR Part 75.303(a) and NIHGPS Chapter 8.3, recipients conducting NIH-supported research covered by this Policy are required to establish and maintain effective internal controls (e.g., policies and procedures) that provide reasonable assurance that the award is managed in compliance with Federal statutes, regulations, and the terms and conditions of award. It is the NIH policy that investigators and others who have access to research records will not disclose identifying information except when the patient participant consents or in certain instances when federal, state, or local law or regulation requires disclosure. NIH expects investigators to inform research patient participants of the protections and the limits to protections provided by a Certificate issued by this Policy.

NIH Data Sharing Policies

As described in section 17, it is NIH policy that the results and accomplishments of the activities that it funds should be made available to the public (see https://grants.nih.gov/policy/sharing.htm). PIs and funding recipient institutions will ensure that all mechanisms used to share data include proper plans and safeguards to protect the rights and privacy of individuals who participate in NIH-sponsored research.

